7.1 DESCRIPTION OF STANDARD OF CARE ASSESSMENTS

Assessments are collected as conducted based on standard of care:

- Demographics and Health History
- Neurological Exam
- Gait
- Pain Score
- Karnofsky Performance Scale (KPS) or Lansky Performance Scale (LPS)
- Engel/ILAE Classification
- Pain Score; documenting head pain
- MRI scans
- Medications: Data collection will include change in dosage, frequency, and the type of medication for the following:
 - o Steroids
 - Anticonvulsants (including antiseizure drugs)
 - Chemotherapy medication
 - Anticoagulation
 - Immunotherapy (e.g. bevacizumab, pembrolizumab)

7.2 REGISTRY REQUIRED QUESTIONNAIRES

Completion of questionnaires is required for this study. Questionnaires may be completed remotely via phone, mail or email if an office visit will not be completed. If a given questionnaire is not completed for a subject at Baseline, analysis of questionnaire data for this subject is not possible. Therefore, if the Baseline Questionnaire is not completed, this questionnaire is not required during follow-up and will not be compensated.

EuroQoI-5D (EQ-5D) (All Subjects 16 years old and older); EuroQoI-5D-Y (EQ-5D-Y) (All subjects 8-15 years old)

The EQ-5D provides simple, generic measure of health for clinical and economic appraisal. This questionnaire consists of 2 pages: 1) the EQ-5D-3L descriptive system and 2) the EQ Visual Analogue scale (EQ VAS). The descriptive system assesses subject's mobility, self-care, usual activities, pain/discomfort, and anxiety/depression. The EQ VAS records the respondent's self-rated health on an approximately 20 cm vertical, visual analogue scale with endpoints labelled 'the best health you can imagine' and 'the worst health you can imagine'. The VAS will be utilized to assess subject pain at the lesion site or on head.

FACT–Br (CNS malignancy subjects only 18 years old and older) **FACT-Peds-Br-Adolescent** (12-17 years old) and **FACT-Peds-Br-Child** (7-12 years old)

Functional Assessment of Cancer Therapy-Brain (FACT-Br) is a commonly used instrument measuring general quality of life that reflects symptoms or problems associated with brain malignancies across 5 scales. FACT-Br is a brain tumor specific 50-item questionnaire for subjects who are not neurologically incapacitated. It will provide an overall QOL score as well as sub-scores for physical well-being, social/family well-being, emotional well-being, functional well-being and concerns relevant to subjects with brain tumors.

QOLIE-31 (Epilepsy subjects only >18 years old): **QOLIE-AD-48** (11-18 years old) **QOLCE-55** (Care Giver provider).

The Quality of Life in Epilepsy Inventory (QOLIE-31) contains seven multi-item scales that tap the following health concepts: emotional well-being, social functioning, energy/fatigue, cognitive functioning, seizure worry, medication effects, and overall quality of life. A QOLIE-31 overall score is obtained using a weighted average of the multi-item scale scores. The QOLIE-31 also includes a single item that assesses overall health.

The QOLIE-AD-48 is a survey of health-related quality of life for adolescents (11-18 years of age) with epilepsy.

The QOLCE-55 is a survey of health-related quality of life for pediatrics answered by their care giver.

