2 ABBREVIATIONS

Abbreviation	Term				
AE	Adverse Event				
CNS	Central Nervous System				
eCRF	electronic Case Report Form				
EDC	Electronic Data Capture				
EQ-5D or EQ-5D -Y	EuroQol-5 Dimensions adult or youth version				
FACT-Br or FACT-Peds-Br	Functional Assessment of Cancer Therapy-Brain adult or pediatric version				
FDA	Food and Drug Administration				
ICF	Informed Consent Form				
ID	Identification Number				
IFU	Instructions For Use				
ILAE	International League Against Epilepsy				
IRB	Institutional Review Board				
KPS	Karnofsky Performance Scale				
LITT	Laser Interstitial Thermal Therapy				
LPS	Lansky Performance Scale				
MRI	Magnetic Resonance Imaging				
NBS	The NeuroBlate [®] System				
OS	Overall Survival				
PFS	Progression Free Survival				
PI	Primary Investigator				
QOL	Quality of Life				
QOLIE-31 or QOLIE-48	Quality of Life in Epilepsy Inventory adult or pediatric version				
SAE	Serious Adverse Event				
VAS	Visual Analog Scale				

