9 PROTOCOL DEVIATIONS

A deviation is defined as an event that did not occur according to the registry protocol. For the purpose of this registry, and in consideration of standard of care practices across study sites, anticipated protocol deviations include: improper consenting of subject (i.e. consent not obtained and improper consenting) and not completing study required questionnaires (if not completed at baseline only one deviation needs to be completed for that subject or if completed at baseline but a subsequent visit or questionnaire is not completed then a deviation for the missed timepoint needs to be completed) A deviation is not required if a questionnaire is not completed because the subject does not meet the age requirement for the validated QOL.

All deviations will be reported to Monteris Medical. It is the site's responsibility to report deviations in compliance with their Institutional Review Board.

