12.1 DATA COLLECTION AND MANAGEMENT

The study data will be hosted in an electric data capture (EDC) system. The EDC system will be compliant with the U.S. regulations, 21 CFR part 11, Electronic Records; Electronic Signatures.

All required data for this study will be collected on standardized Case Report Forms (CRFs).

Qualified study staff at each investigational site will perform primary data collection drawn from source document (e.g. hospital chart) review. All CRFs will be subject to review for omitted data, gross data inconsistencies, illegible data, and deviations. Any deficiencies or deviations will be reviewed, and any necessary action determined (e.g. data query, communication to the study center).

Data review (including crosschecks) will be performed and any discovered errors will be reported to the study site using the data correction and query process (as necessary). The study site will review the query, respond, and make any necessary corrections or comments. The data cleaning cycle will be repeated until all data are considered clean.

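### Section 7.2 of the protocol assigns a VAS to head or lesion-site pain, but the only VAS it describes is the EQ VAS of overall health

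*Protocol*

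**What the plan says.** Section 7.2 of the protocol presents the EQ-5D as a two-page questionnaire: a descriptive system of five dimensions, one of them pain/discomfort, and the EQ VAS. It describes the EQ VAS as a vertical scale of self-rated health "with endpoints labelled 'the best health you can imagine' and 'the worst health you can imagine". The sentence that follows, in the same paragraph, is "The VAS will be utilized to assess subject pain at the lesion site or on head".

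Pain also appears elsewhere as a separate assessment. Section 7.1 lists a Pain Score twice, once without qualification and once as "Pain Score; documenting head pain". Table 1 in Section 7.4 gives Pain Score a row of its own, apart from the EQ-5D row. Section 14 lists pain scores and completed questionnaires as different source documents.

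The two are collected under different rules. For Section 7.1 items, "Assessments are collected as conducted based on standard of care". For Section 7.2 items, "Completion of questionnaires is required for this study", and Section 9 counts "not completing study required questionnaires" among the anticipated deviations.

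**The concern.** A rating of overall health and a rating of pain at a particular place are different constructs. A subject with little head pain can rate overall health as poor, and the reverse is also possible. The EQ-5D paragraph describes the first and then assigns it the job of the second.

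Someone following the text literally could go wrong in one of two ways. They could report EQ VAS values, answered as health, under the label of pain. Or they could present the item to subjects as a pain question, so that the answers could no longer be summarised as self-rated health. The second would touch quality of life, which is the subject of Objective 4. That objective names no instrument, so linking the EQ VAS to it is an inference, though a reasonable one. A descriptive table of means and standard deviations would not reveal either mistake.

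**Working it through.** The plan gives no figure to reproduce on this point. The check is a reading of every mention of VAS, EQ-5D and pain in both documents.

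**Step 1: is any other VAS described?** The abbreviation VAS occurs four times.

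| Place | Use | Pain scale described? |
|---|---|---|
| Protocol Section 2 | Expanded only, as "Visual Analog Scale" | No |
| Protocol Section 7.2 | EQ VAS, named as page 2 of the EQ-5D | No |
| Protocol Section 7.2 | EQ VAS, described as self-rated health | No |
| Protocol Section 7.2 | The sentence assigning a VAS to pain | No anchors or form given |

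The SAP mentions neither VAS, EQ-5D nor pain. The only VAS with a stated construct and anchors is therefore the EQ VAS, and its anchors refer to health at both ends.

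**Step 2: does pain have its own measure?** Yes. Table 1 schedules the two assessments as follows, counting the annual visits after month 12 as years 2, 3, 4 and 5:

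- Pain Score: baseline, discharge, 1, 3, 6 and 12 months (6), plus 4 annual visits = 10 timepoints.
- EQ-5D: baseline, 1, 3, 6 and 12 months (5), plus 4 annual visits = 9 timepoints.

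All 9 EQ-5D timepoints are also Pain Score timepoints, and discharge (10 − 9 = 1) has the Pain Score only. These counts show that the protocol treats the two as separate assessments. They do not measure harm: the Pain Score stays scheduled at all 10 timepoints whatever the disputed sentence means.

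**Step 3: what does each reading of the sentence imply?**

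- *It means the EQ VAS.* It then contradicts the description immediately before it, and a health rating is called pain.
- *It means a separate pain VAS used for the Pain Score.* EQ VAS values are then unaffected. But the sentence sits under the wrong questionnaire, and Section 7.1, where the Pain Score is listed, names no scale.

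The text needs reconciling under either reading. Only the first puts data at risk.

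**The case against.** The strongest reply is that the sentence is simply misplaced. The paragraph says EQ VAS twice and then drops the prefix. The abbreviation list carries the generic term. Section 14 separates pain scores from questionnaires, and the Pain Score exists independently. This reading is plausible and may well be the intended one. It does not rescue the text, because no pain VAS is described for the sentence to refer to.

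A second reply is that the printed form protects the data. A subject who completes a scale labelled with best and worst health rates health, whatever the protocol says afterwards. Under Section 12.1, "All required data for this study will be collected on standardized Case Report Forms (CRFs"), and those forms are not among the documents. This stands: the harm depends on wording that cannot be seen here.

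Some stronger readings are tempting and are not supported:

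- *Sites collected the EQ VAS as pain.* Nothing in either document shows this.
- *The schedules and completion rules conflict.* They differ, but that is a conflict only if the VAS and the Pain Score are meant to be the same thing. Two instruments may have different visits and different rules.
- *The site rated conflicts.* Section 7.1 speaks of head pain, and Section 7.2 of the lesion site or head. For a device that treats brain tissue the difference is trivial.
- *Two pain values at one visit is itself a fault.* The design already has this, since the EQ-5D contains a pain/discomfort item alongside the Pain Score.

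**Conclusion.** The point holds as an error of wording in an assessment instruction. Section 7.2 defines the EQ VAS as a health rating and then gives a VAS the task of measuring pain, with no pain VAS described anywhere. Taken literally the instruction is wrong. Taken charitably it is in the wrong place.

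The impact is minor. Pain is not a named objective, Section 10 specifies descriptive statistics with no hypothesis, and safety, survival and seizure results do not depend on it. No data are affected if sites gave the EQ VAS with its health endpoints and recorded pain as the Pain Score. If the item was presented as pain, the affected EQ VAS values could not be used as self-rated health. The documents do not say which happened, so the number of affected records cannot be estimated. A reader might infer that the registry's quality of life data are compromised; the documents do not support that.

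**What to change.** 1. Delete the sentence from the EQ-5D paragraph of Section 7.2. If a separate pain VAS is intended, move the sentence to the Pain Score entry in Section 7.1 instead.
2. State that the EQ VAS is administered and summarised only as self-rated overall health.
3. State that head or lesion-site pain is reported from the Pain Score in Table 1.
4. Check how the eCRF words the item. If any VAS was answered as pain, keep those values out of the EQ VAS summaries.
5. Reconcile the two Pain Score entries in Section 7.1. The single row in Table 1 suggests duplication but does not settle it: one entry could be general pain and the other head pain. The sponsor should say which before either is removed.

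The cost is a few lines of protocol text and one check of the eCRF. No visit or assessment is added. The downside is that the Pain Score is collected as conducted under standard of care, so it may be less complete than the required EQ-5D, and its scale may vary by site.

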7.3 ADDITIONAL NEUROBLATE PROCEDURES

In the case additional NeuroBlate[®] procedures are performed following the index procedure, this information will be collected on the Additional Procedure form. Any adverse events associated with these procedures will be collected on an Adverse Event form. Patient follow up schedule is based on the index procedure date. Procedure data and reportable adverse events will be collected on all additional NeuroBlate[®] System procedures completed after the Index Procedure.

7.4 VISIT SCHEDULE AND DATA COLLECTION

Table 1 summarizes the study visit schedule and data collection.

	Baseline	Index Procedure	Discharge	1M	3M	6M	12M	Annual visits through 5 yrs.
Demographic and Medical History / Epilepsy Etiology	х							
Neurological Exam	х		х	х	х	х	х	Х
Gait	Х		х	х	х	х	х	Х
Pain Score	Х		х	х	х	х	х	Х
Medication	х	х	Х	х	х	х	х	Х
KPS or LPS (Brain Malignancy only)	Х		х	х	Х	х	х	Х
FACT-Br or Peds-FACT-Br or QOLIE-31 or QOLIE-48	Х			х	х	х	х	Х
EQ-5D or EQ-5D- Y	x			х	х	х	х	Х
MRI		X (Pre and post-op)						
Index Procedure Data		х						
Reportable Adverse Events		х	х	х	х	х	х	Х
Engel/ILAE Classification (Epilepsy subjects Only)				х	Х	х	х	х
Additional Procedure Data		х	х	х	х	х	х	Х
End of Study	End of Study form will be completed upon subject study completion or subject withdrawal (See Section 7.5)							

Table 1. Study Visit and Data Collection Schedule

7.5 STUDY COMPLETION OR WITHDRAWAL

Subjects will complete the study once their 5-year follow-up visit is completed or if the subject was prematurely withdrawn prior to their 5-year visit.

The subject may be prematurely withdrawn from the study for the following reasons:

- Subject did not have NeuroBlate[®] Procedure.
- Subject Lost to Follow-up: All efforts shall be made to document at least 3 attempts to contact subject, which would include a certified letter to the subject. If attempts to contact the subject fail, the subject may be withdrawn from the study and considered lost to follow up.
- Subject Withdrawal: A subject may voluntarily withdraw from the study at any time.
- Investigator Withdrawal of Subject: An Investigator may withdraw a subject for reasons which may include noncompliance, failure to keep appointments, etc.
- Subject Death: If subject passed away, the expiration date will be considered the end of study date. All feasible attempts should be made to confirm date of death, as this is key for overall survival analysis.

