7 STUDY VISITS

A subject follow-up schedule is intended to align with typical standard of care practices. Data may be collected during in-office subject visits or remotely (e.g. telephone, email, or mail), when feasible and appropriate. These modes of data collection aim to help facilitate robust and reliable long-term surveillance and survival data collection. For this standard of care registry, the visit windows are continuous, however target visit dates are provided below. Visits should be completed near the target visit date or be the most complete visit within the visit window. A visit window tool is available in the EDC system. Figure 1 indicates the sequence of subject visits.

Target Visit Dates:

- Baseline within 60 days prior to the Index Procedure
- Index Procedure Day 0
- Discharge N/A
- 1 Month Follow-up Visit Day 30
- 3 Month Follow-up Visit Day 90
- 6 Month Follow-up Visit Day 180
- 1 Year Follow-up Visit Day 365
- 2 Year Follow-up Visit Day 730
- 3 Year Follow-up Visit Day 1095

- 4 Year Follow-up Visit Day 1460
 5 Year Follow-up Visit Day 1825

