Statistical Plan
June 2020

NCT02392078

LAANTERN Statistical Methods

General Summary

Descriptive statistics will be used to summarize the patient population data, operative data, and follow-up data. For continuous variables, the total count, mean, standard deviation, minimum, and maximum will be provided. For categorical variables, the total count and percentage will be provided.

Survival Analysis with Censoring/Truncation

The survival analysis will be used to estimate time-to-event probability and will take into account right-censoring or left truncation. Left truncation occurs when patients are enrolled into the study after the NBS Index Procedure occurs. The survival function will be estimated using the Kaplan-Meier method. The hazard rate over time may be provided along with corresponding 95% confidence limits to assess potential time-dependent trends.

Comparative Analysis

Comparisons in survival/event rates may be made between subgroup of patients with various disease states (for example, epilepsy vs tumor, etc.), differences in baseline demographics, product models (for example, new device iterations, etc.), or other factors that are deemed important for understanding patient outcomes or risk.

Proportional Hazards Regression

The proportional hazards regression models may be used for time-to-event analysis. Predictors may include patient baseline variables in addition to the risk factor of interest.

Determination of Patients for Analysis

All enrolled patients who had procedures with the NBS will be included in this analysis. Additional analyses may be performed for subgroups of interest based on all enrolled patients with valid data.

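### Investigator withdrawal for missed visits ends survival follow-up, with no vital-status check afterwards; overall survival would be overstated if missed visits track decline

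*Protocol*

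**What the plan says.** Protocol Section 7.5 lists the routes by which a subject may leave early. The investigator route reads: "An Investigator may withdraw a subject for reasons which may include noncompliance, failure to keep appointments, etc". The opening of that section makes early withdrawal a form of completion: "Subjects will complete the study once their 5-year follow-up visit is completed or if the subject was prematurely withdrawn prior to their 5-year visit". Table 1 in Section 7.4 adds only a form: "End of Study form will be completed upon subject study completion or subject withdrawal".

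Two safeguards appear in Section 7.5, each attached to a different route:

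- Under loss to follow-up: "All efforts shall be made to document at least 3 attempts to contact subject, which would include a certified letter to the subject".
- Under subject death: "All feasible attempts should be made to confirm date of death, as this is key for overall survival analysis".

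Neither is extended to subjects withdrawn by the investigator.

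Section 7 allows remote contact: "Data may be collected during in-office subject visits or remotely (e.g. telephone, email, or mail), when feasible and appropriate". It also gives the purpose: "These modes of data collection aim to help facilitate robust and reliable long-term surveillance and survival data collection".

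OS is listed under Objective 3 in Section 5.1. On the analysis, the SAP (Survival Analysis with Censoring/Truncation) says: "The survival function will be estimated using the Kaplan-Meier method". It mentions right-censoring. It gives no censoring date for OS, no rule by reason for leaving, and no sensitivity analysis for censoring related to prognosis.

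**The concern.** Kaplan-Meier and proportional hazards estimates assume that subjects censored at a given time have the same later risk of death as those still followed. A clause that lets a site end participation because a subject stopped attending can break that assumption. In a malignancy cohort, failing function is one obvious reason for not attending.

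Such a subject may leave the registry shortly before dying. The investigator route carries no stated duty to attempt contact, and the effort to confirm a death date is written for subjects already known to have died. Follow-up on a named outcome could therefore stop by site discretion, at up to 50 sites, when the information was still obtainable by chart or telephone. A larger registry would not shrink a bias of this kind.

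**Working it through.** **No figure to reproduce.** The documents state no withdrawal rate, survival rate or event count. All rates below are assumptions, used to show direction and a range of size.

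**Step 1: does the sign follow from the rule?** Take a two-state model in which subjects are stable, then declining, then dead. Let *a* be the yearly rate of decline, *hS* and *hD* the death rates when stable and declining, and *wS* and *wD* the withdrawal rates, with withdrawal treated as censoring. The proportions still under observation follow

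s′ = −(a + hS + wS)s and d′ = a·s − (hD + wD)d.

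The large-sample Kaplan-Meier value is exp(−∫(hS·s + hD·d)/(s + d) dt). True OS is s + d with wS = wD = 0.

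- Scenario A: a = 0.9, hS = 0.1, hD = 2.0. True OS is 57.7% at 1 year and 24.1% at 2 years.
- Scenario B: a = 0.4, hS = 0.05, hD = 1.0. True OS is 83.4% and 60.4%.

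Error in Kaplan-Meier OS, in percentage points (1 year / 2 years):

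| Withdrawal rates per year | A | B |
|---|---|---|
| Equal, 0.15 in both states | 0.0 / 0.0 | 0.0 / 0.0 |
| Declining 2 times as often (0.2 v 0.1) | +0.5 / +0.8 | +0.3 / +0.9 |
| Declining 5 times (0.5 v 0.1) | +1.9 / +3.3 | +1.0 / +3.5 |
| Declining 10 times (1.0 v 0.1) | +4.1 / +7.2 | +2.1 / +7.2 |
| Stable 2 times as often (0.2 v 0.1) | −0.5 / −0.8 | −0.3 / −1.0 |
| Stable 5 times (0.5 v 0.1) | −2.0 / −3.3 | −1.1 / −4.1 |

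The sign depends entirely on who is withdrawn.

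**Step 2: a near-worst case.** Assume exponential survival with median 12 months, so λ = ln 2/12 = 0.05776 per month, S(t) = exp(−λt) and S(24) = 25%. A share q of subjects is marked for withdrawal exactly 2 months before death. Marked subjects who die in the first 2 months are kept as observed deaths.

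- After month 2, the subjects at risk number S(t)[(1 − q) + q·S(2)] and observed deaths occur at rate (1 − q)λS(t), with S(2) = 0.8909. The apparent hazard is λ·r, where r = (1 − q)/[(1 − q) + 0.8909q].
- In months 0 to 2, all deaths are observed and those at risk number S(t) − q[S(2) − S(t + 2)]. Integrating λS(t) over that quantity gives the cumulative hazard H₁.
- Apparent 2-year OS = exp(−H₁ − 22λr), with 22λ = 1.2708.

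| q | r | H₁ | 22λr | Apparent 2-year OS |
|---|---|---|---|---|
| 5% | 0.9552 | 0.1158 | 1.2139 | exp(−1.3297) = 26.5% |
| 10% | 0.9099 | 0.1162 | 1.1563 | exp(−1.2725) = 28.0% |
| 20% | 0.8179 | 0.1168 | 1.0393 | exp(−1.1561) = 31.5% |

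The errors are about 1.5, 3.0 and 6.5 points. As the lead time shrinks to zero, r tends to 1 − q and apparent OS to 0.25^(1 − q), which is 26.8%, 28.7% and 33.0%. The 2-month case is therefore close to the ceiling for a share spread evenly over all subjects.

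**Step 3: with vital status kept.** If every withdrawn subject's vital status is obtained, withdrawal no longer censors OS. The Kaplan-Meier limit then equals true OS, and the error is zero in every row above.

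**The case against.** The strongest reply is that the documents do not show who misses appointments. No section links non-attendance to decline, and the registry enrols subjects with any neurological disorder treated with the system, including epilepsy, where a subject doing well may also stop attending. A reader might infer that the rule makes Kaplan-Meier overstate OS. The documents do not support that as a statement of fact: the table in Step 1 shows zero or negative error under other patterns. The Step 2 figures also build in the unfavourable pattern, because every withdrawal is placed just before a death.

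Other points have force:

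- **Existing mitigation.** Remote contact is allowed expressly to support survival data, visit windows are continuous, and Section 5.2 excludes subjects expected to be inaccessible. A missed appointment need not mean lost data. This reduces the risk, but only while the subject remains in the registry.
- **Other exits.** Voluntary withdrawal and loss to follow-up raise the same issue. A reader might infer that the investigator route is the main source of the problem; nothing in the documents shows that. Deleting the clause alone would leave non-attenders free to exit as lost to follow-up. The investigator route differs in having no stated contact duty and in being avoidable.
- **Censoring date.** Censoring at withdrawal is an inference, since neither document gives the OS censoring date. It is the natural reading when withdrawal counts as completion and nothing is collected afterwards.
- **Descriptive purpose.** Section 10 states no hypothesis, and OS has no decision threshold. That limits the consequence. It does not make a biased survival curve harmless in a registry whose objectives are designed for publication.

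**Conclusion.** The plan permits avoidable, and possibly informative, censoring of a named outcome. Section 7.5 lets follow-up stop for non-attendance, treats that as completion and provides no vital-status check afterwards, while calling date of death key for OS.

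The direction and size are conditional. Upward bias needs withdrawal to be commoner among declining subjects, which is plausible in the malignancy cohort but not established. On the Step 2 assumptions, a true 2-year OS of 25% would appear as about 26.5%, 28.0% or 31.5% for shares of 5%, 10% or 20%. These are near-worst illustrations, not estimates, and the shares have no source in the documents. With withdrawal unrelated to prognosis the error is nil, and with more well subjects leaving it is negative.

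The change is worth making because it is cheap and protects OS whichever pattern occurs.

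**What to change.** 1. In Section 7.5 and on the End of Study form, record stopping visits and questionnaires separately from withdrawing consent. Do not let non-attendance or noncompliance end survival follow-up.
2. For subjects withdrawn by the investigator or lost to follow-up, where consent allows, keep recording vital status and date last known alive, by chart review or telephone, at each annual target date to day 1825.
3. In the SAP, censor OS at the date last known alive, and report withdrawals by reason and disease cohort. Some subjects will still be untraceable or will have withdrawn consent, and this lets readers judge how far their censoring could matter.

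The cost is revised wording in the protocol, SAP and form, plus a brief annual check per affected subject by existing site staff. It uses remote contact and chart review, which Sections 7 and 12.1 already allow. The consent form was not available for this review, so its wording should be checked to confirm that it covers continued chart or telephone follow-up.
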